#### Précis:

#### Objective

The Behavioral Neurology Unit studies the human brain systems underlying learning and adaptation with the ultimate goal of finding interventions to make these processes more efficient. We are interested in whether repetitive transcranial magnetic stimulation (rTMS) can alter functional connectivity (FC) and behavioral efficiency in two memory networks in the brain: the hippocampal network, which supports the storage and retrieval of recallable facts, concepts, and events, and the striatal network, which supports the storage and retrieval of skills and habits. Additionally, because these networks interact behaviorally and can interfere with each other, an important question is whether neuromodulation of one network changes connectivity and efficiency in the other network. Pilot data from our group suggest that exogenous stimulation of one network causes it to expand its range of FC and co-opt resources from the other, which is a potential mechanism for the observed behavioral interaction. This study is designed to test a) whether rTMS- modulates within-network FC and memory supported by that network, and b) whether this also causes FC and behavioral changes in the other network.

**Study population:** Healthy Volunteers

#### Design

This study contains four between-subjects experiments and is a mixed inter-/intra subject design. Experiment 1 will use nominally excitatory stimulation targeting the hippocampal network to increase FC within the hippocampal network. We also expect to increase FC between the hippocampal and striatal networks, increased declarative memory, and a possible decrease in procedural, learning. Experiment 2 will use excitatory stimulation targeted to the striatal network. We expect this to cause stronger within-network FC in the striatal network, increased FC between the hippocampus and the striatal network and concomitant behavioral effects. Experiments 3 and 4 will be similar except that we will target nominally inhibitory stimulation to these networks and look for the inverse results. FC will be measured under resting and task-activated conditions and active rTMS will be compared to vertex sham.

#### Outcome measures

The primary outcome measure is the change in FC produced by rTMS within the targeted network. Between-network FC changes and corresponding memory changes will be secondary outcomes. Exploratory measures will include correlations between individual cognitive differences (questionnaires and NIH Toolbox scores), and our primary and secondary outcome measures.

## List of Abbreviations

rTMS	repetitive Transcranial Magnetic Stimulation
fMRI	functional Magnetic Resonance Imaging
BOLD	Blood-Oxygen Level Dependency
FC	Functional Connectivity
rsFC	resting-state Functional Connectivity
tbFC	task-based Functional Connectivity
WPT-F	Weather Prediction Task Feedback Version
WPT-O	Weather Prediction Task Observational Version
ARSQ	Amsterdam Resting-State Questionnaire

## 1. Introduction and Background

### a. Background

Memory deficits are among the most debilitating problems in neurology (Nestor et al., 2005; Vakil, 2005), reduce quality of life for caregivers (Kreutzer et al., 1994), and tax the American public financially (e.g., \$80-100 billion/yr for Alzheimer disease; CDC & NCCDPHP, 2000). Memory is affected disproportionately among cognitive functions in traumatic brain injury (TBI; Levin et al., 1988) and an estimated 3.2-5.3 million Americans are living with a TBI-related disability (Frieden et al., 2015). Because there are no accepted methods for improving memory in amnestic patients, new approaches are urgently needed. Additionally, the rise in popularity of “brain training” indicates a growing interest in improving memory amongst healthy adults (Rabipour & Raz, 2012). While behavioral approaches such as brain training have gained popularity, their utility to everyday human function is controversial (Simons et al., 2016).

Cognitive functions, such as memory, reside in brain networks (Power et al., 2011) and brain disorders disrupt these networks, causing effects on behavior (Gratton et al., 2012). The two characterized memory networks are the striatum-centered memory system (Keele et al., 2003; Knowlton et al., 1996), and 2) the hippocampal-centered memory system (Knowlton et al., 1996; Raichle et al., 2001). The striatal system supports the encoding and retrieval of skills and habits through repetition (e.g., riding a bike; procedural memories), whereas the hippocampal system supports the encoding and retrieval of recallable facts related to objects, events, or concepts (e.g., knowing a bike has two wheels; declarative memories). Although commonly discussed as discrete systems, they interact (Mattfeld & Stark, 2010, 2015; Poldrack et al., 2001), and learning typically involves both declarative and procedural acquisition. (Ghilardi et al., 2009). Evidence from neuroimaging (Mattfeld & Stark, 2010, 2015; Poldrack et al., 2001), behavioral studies in healthy subjects (Ashby & Crossley, 2010; Foerde et al., 2006, 2007) and patients (Foerde et al., 2013; Moody et al., 2004), and lesion experiments in rats (Lee et al., 2008; Packard & McGaugh, 1996), support a competitive relationship between systems. For example, engaging in learning of one memory type can interfere with learning of the other (Brown & Robertson, 2007; Cohen & Robertson, 2011).

rTMS has been shown to improve declarative memory (Wang et al., 2014; Figure 1), but it is unknown whether this enhancement is associated with behavioral effects on procedural memory or whether modulation of the striatal network affects declarative memory. Although TMS has been used to show a double dissociation between stimulation of different cortical sites and their effects on procedural and declarative memory (Cohen & Robertson, 2011; Galea et al., 2010), these studies did not include a measure of target engagement. Therefore, these studies cannot be considered mechanistically informative. To optimize the effect of rTMS on learning and memory, a mechanistic understanding of how these improvements occur is required. We will attempt to fill this gap by using functional connectivity (FC) as a marker of target engagement, and measuring changes in procedural and declarative learning. Because understanding mechanistic changes are necessary to optimize the effect on behavior, changes in FC will serve as our primary outcome measure.

[figure not shown]

Figure 1. Results from Wang et al. (2014) demonstrating stimulus-dependent changes in associative memory. Panel A demonstrates the task used. Twenty face-name pairs were observed by participants during the study phase of the task. During the test phase, the faces were shown and the participant was asked to recall the corresponding word. Panel B indicates the results from baseline, after 3 days of stimulation, and 24 hours after the 5th day of stimulation for real and sham stimulation. Results are shown in proportion to baseline. \* -  $p < 0.05$ , \*\*- $p < 0.01$

FC is stable across scanning sessions within individuals (Barch, et al., 2013; Finn, et al., 2015). Data from 126 participants collected from the Human Connectome Project (Van Essen, et al., 2013) were used to demonstrate that participants' pattern of rsFC can be reliably identified amongst sets of participants and across days (Finn, et al., 2015). For example, Finn and colleagues (2015) demonstrated that a machine classifier can identify whole brain patterns of rsFC across resting sessions with a success rate of at least 92.9% (see Figure 2). High test-retest reliability has been found in several studies (Biswal, et al., 2010; Shehzad, et al., 2009; Zuo, et al., 2010; Zuo, et al., 2010) and the temporal and spatial measures of resting-state networks are stable across years (Choe, et al., 2015). Thus, we are confident that FC is stable enough to use as a biomarker for the effects of rTMS in serial test sessions.

[figure not shown]

Figure 2. Results from Finn et al. (2015). Correct identification scores for machine classifier (y-axis) across eight different networks (x-axis) for FC patterns pulled from R1 and compared to the second session (R1; black bars) and for patterns pulled from the second session and compared to the first session (R2; gray bars). 1 = Medial Frontal, 2 = Frontoparietal, 3 = Default Mode, 4 = Subcortical-Cerebellum, 5 = Motor, 6 = Visual 1, 7 = Visual 2, 8 = Visual Association

TMS is a widely-used method to manipulate the “excitability” of brain pathways (Chen et al., 1997; Huang et al., 2005; Pascual-leone et al., 1994). Despite the limited radius of the effective electromagnetic

field, rTMS affects network-level activity beyond the site of stimulation (Fox et al., 2012). By applying rTMS to a cortical site known to be connected to a network of interest, it is possible to modulate the FC of that network (Eldaeif et al., 2011; Rahnev et al., 2013; Steel et al., 2016; van der Werf et al., 2010; Vercammen et al., 2010). Wang, and colleagues (2014) delivered nominally excitatory (20 Hz) rTMS to the subject-specific posterior parietal cortex (PPC) site that was maximally connected to the anterior hippocampus and observed robust increases in hippocampal network FC. Specifically, this technique increased resting-state FC (rsFC) between the hippocampus and several cortical regions (Fig. 3 Image showing Stimulation-dependent enhancement of hippocampal network). These changes were specific to the hippocampal network, and not the local site of stimulation, as the voxels throughout the brain with the highest baseline FC with the hippocampus showed the largest FC increase. Furthermore, these effects were present two-weeks later (Wang & Voss, 2015). The validity of using rsFC of a cortical area with a deep node (the hippocampus) as a subject-specific targeting guide and then using the change in FC as an outcome measure has been established by Wang et al (2014) and confirmed in our laboratory (see pilot data below).

Using this technique, we will attempt to increase and decrease FC within the hippocampal and striatal memory systems by selectively targeting each network with rTMS in separate experiments. We predict that rTMS will cause changes in FC and memory in the targeted network, which correspond with the stimulation protocol: Nominally excitatory stimulation will cause enhancement of the targeted network, and nominally inhibitory stimulation will cause FC to decrease. Additionally, because these networks are known to interact in behavioral and imaging experiments (Brown & Robertson, 2007; Cohen & Robertson, 2011; Mattfeld & Stark, 2010, 2015; Poldrack et al., 2001), we expect that altering the function of one network will cause changes in the pattern of FC in the other. Pilot data from our laboratory (Fig. 4 Connectivity changes with left Precuneus and medial Occipital Cortex) show that declarative

network FC enhancement is accompanied by significantly increased rsFC between the striatum and the hippocampal network. “Capture” of one system by the other is a good explanation for why behavioral engagement in one learning type interferes with the other (Brown & Robertson, 2007; Cohen & Robertson, 2011).

### b. Pilot Data

Pilot data from our laboratory show that enhancing the hippocampal network with rTMS via the PPC (Wang et al., 2014) is effective and replicable: Nine subjects tested showed significant FC increases between the hippocampus and regions that showed a group-level increase in FC with the hippocampus in Wang et al. (precuneus and medial occipital cortex;  $t(8) = 2.73, p < 0.05, d = 0.75$ ; Fig. 4). To show that these effects were specific to the hippocampus, we calculated FC changes between the dorsolateral prefrontal cortex and the same regions (i.e. precuneus and medial occipital cortex), and found no change from pre- to post-stimulation ( $p = 0.22$ ). Furthermore, the increase in hippocampus FC with the precuneus/medial occipital cortex were significantly greater than the change in global connectedness of the brain ( $t(8) = 2.62, p < 0.05, d = 0.58$ ), showing that these effects were network-specific.

These pilot data, however, also suggest rTMS targeted to the hippocampus and connected areas also affects the striatal network. Figure 4 shows statistically significant FC increases between the *caudate* and the precuneus/medial occipital cortex. Thus, in addition to increasing FC in the hippocampal network, rTMS also caused the striatum to be pulled into tighter association with the hippocampal network.

[figure not shown]

Figure 3. Hippocampal FC changes from Wang et al. (2014)  
Stimulation-dependent enhancement of hippocampal network overlaid on a template brain from Wang et al. (2014). The highlighted regions represent the areas that increased in FC with the hippocampus caused by PPC stimulation.

Structural equation modeling, which can be used to determine the direction of influence between network nodes, indicated a robust increase in connectivity from the striatum to the precuneus and medial occipital cortex after stimulation. This may explain why behavioral engagement of the hippocampal network interferes with procedural learning (Brown & Robertson, 2007; Poldrack et al., 2001). Based on these preliminary findings, we will guide rTMS to the hippocampal network and examine the effects on both the hippocampal-dependent memory system and the striatal memory system. We will also target the striatal network, and look for similar effects on the hippocampal network.

**Figure 4: Hippocampal FC changes from pilot data.**

[figure not shown]

Figure 4. Pilot data (N=9) demonstrating increases in FC between precuneus and medial occipital cortex and three separate brain regions.

\* -  $p < 0.05$

#### c. Resting-State vs. Task-Based Connectivity

The results of Wang et al. (2014) and data from our laboratory show that rTMS can enhance rsFC within a targeted network. However, it is unknown whether the same is true of tbFC. Because tbFC may be a better measure of stimulation-induced changes, we will include this measurement in our experiments and compare the results to rsFC.

#### d. Measuring mentation during resting-state scans.

Recent work has revealed that mentation patterns during resting-state scanning correlates with FC measurements (Gregory et al., 2016). Because differences in mentation between participants are difficult to control and could potentially explain our results, we will include a measure of mentation (the Amsterdam Resting-State Questionnaire) as an exploratory measure to our protocol.

## 2. Study Objectives

The overall objective of this study is to determine whether the hippocampal and striatal memory networks can be modulated using rTMS. We will also examine cross network changes in FC by guiding nominally excitatory and inhibitory stimulation to the striatal and hippocampal memory networks and measuring the effects on both the targeted and non-targeted one. The results will be used to inform future clinical trials of rTMS in patients with disorders of learning and memory and possibly to enhance and accelerate learning in healthy individuals.

#### a. Primary aims

**Primary Aim 1:** Determine whether nominally facilitatory stimulation of the hippocampus increases rsFC or tbFC within the hippocampal memory network (Experiment 1; Replication of Wang et al., 2014).

**Primary Aim 2:** Determine whether nominally facilitatory stimulation of the striatum increases rsFC or tbFC within the striatal memory network (Experiment 2).

**Primary Aim 3:** Determine whether nominally inhibitory stimulation of the hippocampus decreases rsFC or tbFC within the hippocampal memory network (Experiment 3).

**Primary Aim 4:** Determine whether nominally inhibitory stimulation of the striatum decreases rsFC or tbFC within the striatal memory network (Experiment 4).

**b. Secondary aims**

Our secondary aims are to measure the effects of each type of stimulation at each site on declarative and procedural learning and memory and between network changes in task-based and resting-state FC.

**c. Exploratory aim**

We will search for predictors of the within and between network FC changes, including scores on the ARSQ, the NIH toolbox, and the procedural and observational versions of the Weather Prediction Task.

### 3. Subjects

**a. Description of study population**

We will study 104 healthy individuals (26 in each experiment). We are requesting up to 122 healthy volunteers as the accrual ceiling to account for dropouts and screening failures. Participants who are withdrawn or drop out from the study will be replaced. NIH employees who are not members of the BNU will be allowed to participate. Based on previous experience, our anticipated dropout rate is 15%.

**b. Inclusion criteria**

- Age 18-40 (inclusive)

**c. Exclusion criteria**

- Any current major neurological or psychiatric disorder such as (but not limited to) stroke, Parkinson disease, Alzheimer disease, schizophrenia or major depression
- History of seizure
- Medications acting on the central nervous system, such as those that lowers the seizure threshold such as neuroleptics, beta lactams, isoniazid, metronidazole; benzodiazepines, tricyclic or other antidepressants; or prescription stimulants.
- Ferromagnetic metal in the cranial cavity or eye, implanted neural stimulator, cochlear implant, or ocular foreign body
- Implanted cardiac pacemaker or auto-defibrillator or pump
- Non-removable body piercing
- Claustrophobia
- Inability to lie supine for 2 hours
- Pregnancy, or plans to become pregnant during the study.
- Members of the NINDS BNU
- Subjects that received rTMS under protocol 17-N-0055 are excluded in order avoid learning effects from previously being exposed to the same behavioral tasks

- Subjects who have contraindications to MRI (we will follow the NMR Center guidelines for MR safety). Some of the exclusions are:
  1. Have non-MRI compatible metal in the body, such as a cardiac pacemaker, brain stimulator, shrapnel, surgical metal, clips in the brain or on blood vessels, cochlear implants, artificial heart valves or ferromagnetic fragments in the eye or oral cavity as these make having an MRI unsafe.
  2. Unable to lie flat on the back for the expected length of the experiment (2 hours).
  3. Have an abnormality on the brain imaging or neurologic examination not related to the diagnosis.
  4. Non-removable body piercing or tattoo posing MRI risk
  5. Pregnancy (urine pregnancy test)

An eligibility checklist is provided in Appendix A.

## 4. Study Design and Methods

### a. Study overview

This protocol will include four experiments, each using rTMS and MRI, in a between-subjects design (Table 1). Experiments 1 and 3 will use PPC rTMS. Experiments 2 and 4 will use M1 stimulation.

	Active Stimulation Type	Active Stimulation Site	Targeted Network
Experiment 1	Facilitatory (20-Hz)	PPC	Hippocampal
Experiment 2	Facilitatory (20-Hz)	M1	Striatal
Experiment 3	Inhibitory (cTBS or 1-Hz)	PPC	Hippocampal
Experiment 4	Inhibitory (cTBS or 1-Hz)	M1	Striatal

Table 1. Experiment Details. PPC = Posterior Parietal Cortex, M1 = Motor Cortex.

Table 2 shows the timeline of each experiment. Each study will include FC and memory testing at baseline, 24-hours after, and two weeks after three days of rTMS. The number of days of rTMS is based on pilot data where three days of stimulation produces significant enhancement of rsFC in the hippocampal network in five out of six individuals tested. Each participant will make a maximum of 6 visits to the lab (not including screening), for a maximum time commitment of 14 hours. The 24-hour follow-up will occur between 12 and 48 hours after the last stimulation session, and the 2-week follow-up will occur 14-21 days after baseline measurements. Scanning will occur in the NIH NMRF. All visits will be outpatient.

	Baseline Day	rTMS Sessions	Post Stimulation Day	2-week follow-up
Group 1	Baseline FC and Memory	Active Stimulation 3-sessions	FC and Memory Testing	FC and Memory Testing
Group 2	Baseline FC and Memory	Vertex Stimulation 3-sessions	FC and Memory Testing	FC and Memory Testing

Table 2. Timeline of each experiment.

**b. Recruitment**

Healthy participants will be recruited from the pool of individuals self-referring to the study directly and via the NIH Clinical Research Volunteer Program. Although NIH employees will be allowed to participate, no direct solicitation of employees/staff by supervisors or co-workers will take place. All recruitment material will be IRB approved. Participants who indicate interest will be pre-screened over the phone. Pre-screening questions are listed in Appendix B.

Healthy participants will be recruited from the pool of individuals self-referring to the study directly and via the NIH Clinical Research Volunteer Program and via advertisements that will be pre-approved by the IRB. Although NIH employees will be allowed to participate, no direct solicitation of employees/staff by supervisors or co-workers will take place. Any recruitment material will be IRB approved. Participants who indicate interest will be pre-screened by phone. Pre-screening questions are listed in Appendix B.

IRB-approved ads will be posted on NIH listservs with the permission of the moderator and IRB required statement on how the receiver was identified. Listservs may include NIH sponsored recruitment list serves such as (NIH HV recruitment list serv). Listserv announcement will include:

*“You are receiving this message because your email address is included in the above NIH Listserv mailing list. The purpose of this message is to inform you of studies that are recruiting volunteers at NIH, Bethesda, Maryland. The moderator of the listserv mailing list has permitted its use for this distribution”.*

**i. Participant rescheduling**

It is likely that some participants will miss some sessions. If this occurs, and the participant is still willing to participate, we will reschedule. If the subject has already received rTMS, we will wait at least 30 days to reschedule the session so that the effects of stimulation wash out. If a participant misses a visit after baseline measures have been collected, besides the two week follow-up visit, baseline measurements (MRI and behavioral assessments) will be performed again. If a participant completes all visits, but is unable to attend the follow-up visit, their attendance in the study will be considered complete.

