### **b. Secondary outcome measures**

- Pre-to-Post rTMS differences in WPT-O scores
- Pre-to-Post rTMS differences in WPT-F scores
- Pre-to-Post rTMS differences in rsFC and tbFC between memory networks.

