## **10. Statistical Analysis**

### **a. Analysis of data/ study outcomes**

Our primary aim is to examine stimulation-dependent changes in FC within the targeted network in each study. Secondary aims for this protocol will include all behavioral change data from the WPT-F and WPT-O and changes in FC to the non-targeted network, and between networks.

To calculate FC from resting-state scans, the Pearson correlation coefficients ( $r$ ) between time courses of BOLD activity in a seed region (i.e. hippocampus or striatum) will be calculated to determine the FC before and after rTMS stimulation. They will be Fisher-transformed to normalize  $r$ -values.

To calculate FC from task-based scans, the time series from a seed region will be inputted into a general linear model analysis as a regressor along with a regressor indicating when the task is occurring. For the WPT-F, this will include both the choice phase and the feedback phase during learning. For the WPT-O, this will include the observational trials and the retrieval trials. This analysis will be performed on each

individual to create a spatial map of beta values indicating the strength of the association between the seed and other regions during task performance.

*Statistical analysis for Experiments 1 and 3 (targeting the hippocampal network)*

iv. Preliminary Aims

Primary Aim 1

To confirm modulation of the hippocampal network, the average timeseries of the left hippocampal seed will be correlated with all other voxels with available data before and after stimulation. These data will be submitted to AFNI's 3dLME linear mixed effects function, which will be used to reveal potential areas of significant change in rsFC and tbFC.

v. Secondary Aims

Secondary Aims

Behavioral data will be submitted to a 3 x 2 x 2 ANOVA using timepoint (Pre-stimulation, post-stimulation, and follow-up), group (PPC vs. Vertex), and learning type (procedural and declarative) as factors. A significant interaction ( $p < 0.05$ ) between time, group, and learning type will confirm network-dependent modulation of each memory type.

To confirm changes in FC, a similar analysis will be performed as Primary Aim 1, except that the timeseries of the right striatum seed will be used instead of the hippocampal seed.

*Statistical Analysis for Experiments 2 and 4 (targeting the striatal network)*

i. Preliminary Aims

Preliminary Aim 1

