### **b. Power analysis (All experiments)**

All experiments in this protocol are powered based on the primary outcome, which relates to modulating FC within the targeted networks.

A power analysis was conducted on our preliminary data using G\*Power v3.1. We used a repeated-measures ANOVA model with FC changes between the hippocampus and the precuneus/medial occipital cortex as my dependent variable. The precuneus/medial occipital cortex was used because these regions showed the most robust response to stimulation in Wang et al., (2014). Based on these data (Mean Difference = 0.16, Pooled Standard Deviation = 0.21, Cohen's  $d = 0.75$ ), and assuming power of 0.80 and  $\alpha = 0.05$ , 26 right-handed healthy participants between 18 and 40 years of age will be needed (13 per group) for each experiment (104 total). To account for attrition (estimated ~15%), we will request an accrual ceiling of 122.

There were no preliminary data to conduct a power analysis for stimulation involving the striatal network. Thus, we propose to have 13 analyzable subjects in the M1 group, the same number as in the parietal group from Experiments 1 and 3. We also plan to obtain 13 subjects in the control group, resulting in 26 analyzable healthy subjects (13 per group).

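### A participant who misses only the 2-week visit counts as complete, but the one test named for the memory outcomes has no stated way to use that participant's baseline and 24-hour scores

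*Combined protocol and SAP*

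**What the plan says.** Section 4.b.i (Participant rescheduling) expects gaps: "It is likely that some participants will miss some sessions". It then treats the 2-week visit differently from the others. The repeat-baseline rule exempts it: "If a participant misses a visit after baseline measures have been collected, besides the two week follow-up visit, baseline measurements" are taken again. For the last visit itself the rule is: "If a participant completes all visits, but is unable to attend the follow-up visit, their attendance in the study will be considered complete".

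Section 3.a states who is replaced: "Participants who are withdrawn or drop out from the study will be replaced". A participant deemed complete is neither withdrawn nor a dropout, so non-replacement is the natural reading, though it is not stated in those words.

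Section 8 (Subject Safety Monitoring) says that data from participants who have done at least the first session, meaning both the scan and the behavioural assessment, are retained and analysed.

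Section 9.b defines the memory outcomes as changes, for example "Pre-to-Post rTMS differences in WPT-O scores", with a matching entry for WPT-F. It does not say which post-stimulation visit is meant. Sections 4.a and 4.d schedule memory testing at baseline, 24 hours and two weeks.

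Section 10.a gives one test for these outcomes: "Behavioral data will be submitted to a 3 x 2 x 2 ANOVA using timepoint (Pre-stimulation, post-stimulation, and follow-up", crossed with group and learning type. The three-way interaction is judged at 0.05. The same test is repeated for Experiments 2 and 4. No missing-data method and no separate pre-to-post contrast is given for the behavioural data. Functional connectivity (FC), by contrast, goes into a linear mixed-effects model (3dLME).

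**The concern.** The conduct rules keep the participant and the data, while the analysis names a method that, in its usual form, cannot use them. Timepoint and learning type vary within a person, so a classical ANOVA of this design needs all 3 x 2 = 6 scores from each participant. Someone with valid baseline and 24-hour scores on both tasks has four of the six. The analyst must then delete that person, impute the missing visit or change the model. The plan does not say which, so the choice would be made after the data are seen.

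Two things are at stake. The first is observed pre-to-post memory data, in experiments of only 26 people each, on the outcomes listed in Section 9.b. The second is present even if nobody misses a visit. The interaction over three timepoints does not directly test a pre-to-post change, because it pools the 24-hour and 2-week departures from baseline into a single test.

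**Working it through.** **The plan's own attrition figure.** Inputs from Section 10.b: 104 analysable participants and about 15% attrition. 104 / (1 − 0.15) = 122.35, against the stated ceiling of 122, so the figure reproduces. This 15% is overall dropout, which the replacement rule covers. It is not the rate at which the 2-week visit is missed, because someone who misses only that visit counts as complete.

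**What the named test needs.** As a check, 26 simulated participants were given three visits and two tasks, with the third visit removed for 4 of them. The data were passed to a standard repeated-measures ANOVA routine with the within-person factors only. It refused to fit, reporting unbalanced data. Those 4 people must be removed or imputed. The observed scores at stake are 4 participants x 2 visits x 2 tasks = 16.

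**Size of the loss.** Inputs: 26 per experiment and 104 in total (Section 10.b). The miss rate q for the 2-week visit is not in the documents, so the range below is an assumption. Expected complete cases are N x (1 − q). The chance that all 26 attend is (1 − q)^26, taking attendance as independent between people.

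| Assumed q | Complete cases per experiment | Complete cases in total | Chance that all 26 attend |
|---|---|---|---|
| 5% | 26 x 0.95 = 24.7 | 104 x 0.95 = 98.8 | 0.95^26 = 0.26 |
| 10% | 26 x 0.90 = 23.4 | 104 x 0.90 = 93.6 | 0.90^26 = 0.06 |
| 15% | 26 x 0.85 = 22.1 | 104 x 0.85 = 88.4 | 0.85^26 = 0.01 |

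If all available visits are used, everyone with baseline and 24-hour scores stays in the pre-to-post comparison whatever q is: 26 per experiment and 104 in total, when follow-up is the only visit missed.

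**Match between test and outcome.** The interaction has (3 − 1) x (2 − 1) x (2 − 1) = 2 degrees of freedom. A pre-to-24-hour change is one of those two. An effect present at 24 hours and gone by two weeks would be tested as part of the pair, not on its own.

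**The case against.** The strongest reply is that nothing in the documents excludes these participants. Section 10.a says only ANOVA. Complete-case deletion is a habit of the classical procedure and not a rule of this plan, and Section 8 points the other way. That stands, and a reader who infers that the plan itself discards the data goes beyond the text. But Section 8 states an intention and supplies no method, and the test that is named cannot carry it out in its usual form.

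It can also be said that the 2-week visit is scheduled for everyone and that the completion rule covers people unable to attend, so the visit is not optional. That is fair. Rescheduling may not rescue it, however: once rTMS has been given, Section 4.b.i asks for a wait of at least 30 days, while Section 4.a places this visit 14 to 21 days after baseline.

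A reader might infer that FC and memory results would come from different people. The documents do not support this. Complete cases would be a subset of the FC participants. The only planned comparison of FC with memory scores is an exploratory correlation (Section 9.c), which does not pass through the ANOVA.

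A reader might also attach a loss of power, or say that the memory test misses its target of "26 analyzable healthy subjects (13 per group". Section 10.b sets that number for FC. No effect size is given for the memory tasks or for the three-way interaction, so any power figure would rest on an invented effect.

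Finally, replacing the ANOVA by separate contrasts for each task would drop the learning-type factor, and with it the test of network-dependent modulation. That objection is right, and any repair must keep the interaction.

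**Conclusion.** The point holds as a mismatch between the conduct rules and the named analysis. A participant without the 2-week visit is complete, by inference not replaced, and promised a place in the analysis. The only test named for the secondary memory outcomes would by default leave that person out, and no alternative is stated. At an assumed miss rate of 5% to 15%, about 25 down to 22 of 26 participants per experiment would remain in a complete-case ANOVA.

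The conclusion rests on reading the ANOVA as the conventional complete-case procedure and on an assumed miss rate that the documents do not give. It concerns secondary outcomes only. The primary FC analysis is described before and after stimulation in a mixed model, so a missed follow-up need not remove anyone there. The change is worth making because a better-suited model of a kind the plan already uses is available at little cost.

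**What to change.** In Section 10.a, for all four experiments, replace the 3 x 2 x 2 ANOVA with a linear mixed model on all available visits. Enter visit as a categorical factor, with group, learning type and their interactions, and a random participant effect. Allow for correlation between a participant's two tasks, for example through a participant-by-task term. Keep the time by group by learning-type interaction at 0.05 as the stated test.

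Add one pre-specified contrast of that interaction, baseline to 24 hours, for the pre-to-post outcomes in Section 9.b, and state there that the 24-hour visit is the one meant. Report the 2-week contrast separately as persistence. State that participants without the 2-week visit stay in, which brings Sections 4.b.i, 8, 9.b and 10.a into line, and report the number of missed follow-ups by group.

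The cost is analysis wording and slightly more analysis work, with no extra participants or visits. The model assumes that missed follow-ups are missing at random given the observed scores, and the plan should say so.
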